Number of Participants with Rationale	The study is planned with 3 study arms. The average initial VAS score after pain induction varies depending on the examination and is an approximation of an initial value of 4.73 ± 2.39 . A reduction in the VAS score after cold application was assumed to be an average of 47%. After taking into account the dropout rate of 10% and splitting into 3 randomized groups, a patient count of 15 subjects per study arm is considered statistically appropriate. The results were determined using the PASS 2023 version 23.0.1 software.
Intervention	The product "Cold Hot Pearls Maxi Pack" of the company Axanova AG is used for testing. This product has a gel bead filling that can be used for cold and heat applications. According to the manufacturer, the cold compresses must be stored in a freezer for at least 1 hour before they can be used. The cold pack can then be placed on the affected area on the fleece side, but for a maximum of 20 minutes in the same place.

	
In our study, there are 2 cooling groups:
 
The first group starts cooling immediately after the muscle soreness protocol.
 
The second group starts cooling 24 hours after the muscle soreness protocol.

Control Intervention	
The control group will not receive an intervention according to the muscle soreness protocol.

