4 STATISTICS AND METHODOLOGY

4.1. Statistical analysis plan and sample size calculation

Sample calculation

Before any data collection is carried out, case number planning and sample size calculation is necessary in order to obtain valid results. In clinical trials and animal experiments, this is even mandatory and is carefully reviewed before approval is granted (MDR, Annex XV, Chapter 1, Section 2.1, DIN EN ISO 14155:2021-05). Postoperative cryotherapy utilizing ice packs, cooling, or continuous cryotherapy devices reduced pain scores on the visual analogue scale and analgesic consumption in about half of the research studies comparing these outcomes against their control (no cryotherapy). The average initial VAS score after pain induction varies depending on the study and is an approximation of a baseline value of 4.73 ± 2.39 . A reduction in the VAS score after cold application was assumed to be an average of 47%. After taking into account the dropout rate of 10% and splitting into 3 randomized groups, a patient count of 15 subjects per study arm is considered statistically appropriate. The results were determined using the PASS 2023 version 23.0.1 software.

Numerical Results for Multiarm Tests for the Difference Between Treatment and Control Agents Assuming Equal Variance

Solve for:	Number of cases
Group distribution:	equal to ($N_c = N_1 = N_2 = \dots$)
Test Type:	T-Test
Hypothesis:	$H_0: \delta = 0$ vs. $H_1: \delta \neq 0$
Number of groups:	3
Bonferroni Correction:	none (divisor = 1)

Comparison	Target Strength	Real	Number of cases	Mean μ_i	Difference δ_i	Standard deviation σ	Alpha
Control			13	4,72		2,1	
vs. A	0,8	0,832 33	13	2,21	-2,51	2,1	0,05
vs. B	0,8	0,912 87	13	1,87	-2,85	2,1	0,05
Total	n/a	n/a	39	n/a	n/a	n/a	n/a

Comparison	The group involved in the comparison between the treatment and control shown in this report row. The comparison is made on the basis of the difference.
Test Strength	The desired test strength. Test strength is the probability of rejecting a false null hypothesis for this comparison. This test strength refers only to the comparison shown in this line.
Really. TS	The test strength that is really achieved.
N_i	The number of elements in the i th group. The total sample size is displayed in the last row of the column.
μ_i	The mean value of the i th group at which the test strength is calculated. The first row contains μ_c , the mean value of the control group.

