δ_i	The difference between the i th treatment agent and the control agent ($\mu_i - \mu_c$) for which the test strength is calculated.
σ	The standard deviation of the responses within each group.
Alpha	The probability of rejecting the null hypothesis that the control mean is equal to the treatment mean described in this row.

Summary statements

A parallel 3-group design (with a control group and 2 treatment groups) is used to test whether the mean for each treatment group is different from the mean of the control group ($H_0: \delta = 0$ versus $H_1: \delta \neq 0, \delta = \mu_i - \mu_c$). The hypotheses are evaluated using two two-sided, two-sample methods. Bonferroni-adjusted t-tests with the same variance and an overall (experimental) Type I error rate (α) of 0.05. The common standard deviation for all groups is assumed to be 2.1. The mean value of the control group is assumed to be 4.72. The treatment means 2.21 and 1.87 with at least 80% test strength to be detected in each case. For the test, the (same) group sample size needed for each of the three groups (control and treatments) is 13 (39 subjects in total). The group sample sizes were calculated using PASS 2023, version 23.0.1.

Sample size taking into account the dropout rate

Group	Dropouts Abandonment Rate	Number of cases/group	Number of cases with drop-out rate	Number of abandoned participants
1 - 3	10%	13	15	2
Total	n/a	39	45	6

Taking into account the drop-out rate

Taking into account a dropout rate of 10%, the group sizes in each study arm should be 15 subjects.

Statistical approach to examine the primary endpoints

The statistical analysis is performed using IBM SPSS Statistics (version 27, IBM Corp., Armonk, NY, USA) and the significance level is set to $p < 0.05$.

In order to be able to determine the differences between groups, a repeated ANOVA analysis is carried out with a factor of 1: time (baseline, 24 hours, 48 hours, 72 hours) and a factor of 2:

intervention (group A, group B, group C) for the recovery parameters (inflammation values, muscle swelling, muscle soreness data, maximum voluntary isometric muscle contraction).

The examination is discontinued if the participants are intolerant to the local cold application. Participants in the IC and DC groups are instructed to cancel a cooling session and contact their contact immediately if they experience symptoms such as severe pain/discomfort as a result of the cooling.

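### The sample-size rationale gives the soreness VAS as 4.73 ± 2.39, but the power calculation uses an unexplained common SD of 2.1; if 2.39 is the SD in every group, power for group A versus control is about 73%, not 83%

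*Combined protocol and SAP*

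**What the plan says.** Two figures for the spread of the soreness VAS stand close together in the sample-size justification.

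- **Rationale.** Section 4.1 says that the score after pain induction "is an approximation of a baseline value of 4.73 ± 2.39". The synopsis (Number of Participants with Rationale) repeats it: the score "is an approximation of an initial value of 4.73 ± 2.39". Neither place says whether ± 2.39 is a standard deviation, and neither attaches a reference to it.
- **Calculation.** The PASS summary in section 4.1 states "The mean value of the control group is assumed to be 4.72" and "The common standard deviation for all groups is assumed to be 2.1". The PASS table lists 2.1 as the standard deviation for the control row and both treatment rows, and its legend defines σ as the within-group standard deviation of the responses.

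The power claim is "The treatment means 2.21 and 1.87 with at least 80% test strength to be detected in each case". The table gives 0.83233 for A versus control (difference -2.51) and 0.91287 for B versus control (difference -2.85), at 13 per group and alpha 0.05 with no Bonferroni division. A 10% dropout allowance then raises 13 to 15 per arm.

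**The concern.** The calculation uses practically the same mean as the rationale (4.72 against 4.73) but not the spread printed beside that mean. The SD used is 12% smaller than 2.39 (2.1/2.39 = 0.879), and the variance 23% smaller (4.41/5.71 = 0.772). A smaller SD raises the computed power. The documents do not derive 2.1 or acknowledge the change.

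At stake is the claim that each cooling group is compared with control at 80% power or more. Group A has the smaller assumed difference, and its printed power exceeds the target by only about 3 points, so a modest rise in the SD takes it below 80%. A non-significant result for A would then be read against a power statement that the plan's own rationale figure may not support. Section 4.2 says that drop-outs are not replaced, so later recruitment cannot make up a shortfall.

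**Working it through.** **Inputs, all from section 4.1.** Differences 2.51 (A) and 2.85 (B); SD 2.1 (table and summary) or 2.39 (rationale); two-sided two-sample t-test with equal variances; alpha 0.05 per comparison; n = 13 per arm, or 15 if nobody drops out.

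**Formula.** Power = P(|T| > t_crit), where T is noncentral t with df = 2n - 2 and noncentrality λ = (δ/SD) × √(n/2). At n = 13, df = 24, t_crit = 2.064 and √(13/2) = 2.550.

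**Step 1: reproduce the plan's figures (SD 2.1, n = 13).**

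- A: λ = (2.51/2.1) × 2.550 = 3.047, power 0.83233. Printed: 0.83233.
- B: λ = (2.85/2.1) × 2.550 = 3.460, power 0.91287. Printed: 0.91287.
- At n = 12, power for A is 0.799, so 13 is the smallest n reaching 80%. Then 13/0.9 = 14.4, rounded up to 15.

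The method is therefore the one used in the plan, and the arithmetic is sound given an SD of 2.1.

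**Step 2: change only the SD, to 2.39 in all groups.**

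| Comparison | SD 2.1, n = 13 | SD 2.39, n = 13 | SD 2.39, n = 15 |
|---|---|---|---|
| A vs control (2.51) | 83.2% | 72.9% (λ = 2.678) | 79.3% |
| B vs control (2.85) | 91.3% | 83.1% (λ = 3.040) | 88.3% |

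At n = 13, A loses about 10 points and B about 8. B stays above 80%. A is below 80% at 13 and just below it at 15.

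**Step 3: how far the SD can rise, and what 13 per arm can detect.**

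- Largest SD that keeps A at 80%: 2.19 with 13 per arm, 2.37 with 15.
- At SD 2.39 and 13 per arm, the difference detectable with 80% power is 2.74 cm, above the 2.51 cm assumed for A.

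**Step 4: sensitivity to method.** For A at SD 2.39 and n = 13, the normal approximation gives 76.3%, and a pooled three-arm error term (df = 36) gives 74.1%. Both are below 80%.

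**Step 5: can 2.39 and 2.1 both be right?** Suppose 2.39 holds for controls only, 2.1 is the root mean square over three equal arms, and the two treated arms share one SD, s.

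- 3 × 2.1² = 2.39² + 2s², so s = √[(13.23 - 5.71)/2] = 1.94.
- A versus control then has SD √[(2.39² + 1.94²)/2] = 2.18, and power of about 80.5% at 13 per arm.

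If 2.1 were instead pooled over one control and one treated arm, s would be √(2 × 4.41 - 5.71) = 1.76. Neither 1.94 nor 1.76 appears in the documents.

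**The case against.** The strongest reply is that the two figures need not measure the same thing. The plan never calls ± 2.39 an SD. It introduces the figure by saying that the average score varies from study to study, so it could describe spread between studies. It also refers to the score before any cooling, whereas 2.1 is meant for all three groups, two of them cooled and with lower assumed means. On the pooling in Step 5, 2.39 in controls and 80% power for A can both hold. The only figure labelled a standard deviation is 2.1, and 2.39 is no better sourced. The calculation's effect sizes also differ from the narrative: reductions of 53% and 60%, against 47%. The PASS inputs may therefore be a separate set.

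All of this stands as a limit on the conclusion. A reader might infer that power for A simply is 73%, or that the plan replaced a known SD with a more convenient one. The documents support neither. The 73% depends on a reading of ± 2.39 that is natural, because the paired mean is practically the PASS control mean, but is not stated. Nothing shows why 2.1 was chosen.

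The printed power also belongs to a two-sample t-test, while the planned analysis is a repeated-measures ANOVA over four time points. Its power depends on a within-subject correlation that the documents do not give, so neither 83% nor 73% is the power of that analysis.

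These points do not remove the inconsistency. Every reading that reconciles the two figures needs a statement or a number that the plan does not contain.

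**Conclusion.** The plan gives two unreconciled figures for the spread of the VAS score that drives its sample size, and the power claim for group A depends on which applies. If ± 2.39 is the between-subject SD in every group, with the printed differences, uncorrected alpha of 0.05 and 13 per arm, power is about 73% for A (79% if all 15 complete) and about 83% for B. The 80% claim then fails for A and holds for B. If 2.1 is a value pooled over three arms with 2.39 in controls, A has about 80.5%, but the plan does not say this.

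The point concerns the SD alone. It does not show that the trial is too small for its planned analysis, and it leaves aside two neighbouring inconsistencies in section 4.1: the 47% reduction against the larger assumed differences, and a table without Bonferroni division beside a summary that mentions it. As printed, the claim of at least 80% power in each comparison is not adequately supported for A.

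**What to change.** In section 4.1 and the synopsis, state what ± 2.39 is (SD or not, within or between studies, which group and time point) and give its source. Reconcile it with 2.1 so that one justified SD is used in the synopsis, text, table and summary.

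- **Unless 2.1 is justified:** keep 15 per arm, restate power at 13 evaluable per arm as about 73% (A versus control) and 83% (B versus control), give the detectable difference of about 2.7 cm at 80% power, and remove the 80% claim for A.
- **If 2.1 is justified and kept:** give its source or derivation and print the 2.39 result beside it as a sensitivity figure.

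The cost is rewording and one rerun of the calculation. No subjects are added and trial conduct does not change. The downside is a less favourable stated power for A.

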
Risk / Benefit Assessment	In this examination, the risk can be classified as minimal. The product is applied as recommended by the manufacturer. The muscle soreness protocol is a protocol that has already been described in the scientific literature.
Objective(s)	The aim of this study is to investigate how local, repeated cold applications affect the recovery phase according to a muscle soreness protocol. Recovery is assessed at 24-hour intervals (up to 72 hours according to the muscle soreness protocol).
Endpoint(s)	
Primary endpoints:
 
 • Sore muscles (VAS 0 – 10 cm) • Inflammation levels (blood sinking velocity, C-reactive protein, creatine kinase) • Muscle swelling (in cm using ultrasound) • Maximum Voluntary Isometric Thigh Contraction (in kg) 
Secondary endpoints
 
 • Surface temperature of the skin (in °C) • Thermal Perception
Investigation Design	Randomized, controlled trial
Statistical Considerations	Repeated measure ANOVA, n=45 subjects
Inclusion- / Exclusion Criteria	
Inclusion Criteria
 
 • Young, healthy adults between the ages of 18 and 30 • No surgical interventions on the musculoskeletal system in the trunk area and lower extremities 
Exclusion criteria
 
 • Current pain conditions: Subjects with acute pain conditions. • Current inflammatory conditions: Presence of inflammation or known inflammatory diseases. • Medication intake (excl. anticonception drugs): Subjects taking medication, with the exception of anticonception drugs. • Pregnant subjects: Women who are pregnant or breastfeeding. • Competitive athletes: Test subjects who practice competitive sports. • Children/adolescents: Subjects under 18 years of age or over 30 years of age. • Non-intact skin conditions (e.g. psoriasis): Skin conditions, such as psoriasis or other non-intact skin conditions. • Known circulatory disorders: Presence of known circulatory disorders. • Cold allergy (Raynaud's syndrome): Allergy to cold or the presence of Raynaud's syndrome. • Previous operations on the upper body or legs: Operations in the areas of the body examined. • Disturbed perception in the thigh: Disturbances in the sensation of temperature or touch in the thigh area. • Diagnosed diseases: Presence of diagnosed diseases that could affect participation in the examination. • Smoking: When the subject smokes.

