2 INVESTIGATION OBJECTIVES AND DESIGN

2.1 Hypothesis and primary objective

The aim of this study is to investigate whether repeated, local cold applications have a positive impact on recovery compared to no intervention. Furthermore, it will be investigated whether cooling, which has been carried out immediately after the exertion, has a more positive influence on the recovery compared to refrigeration that has started 24 hours after the exertion. The ability to recover is determined on the basis of the following parameters: muscle soreness, inflammation levels, muscle swelling and maximum voluntary isometric contraction of the thigh muscles.

- H0A: There is no significant difference between repeated cold applications and the control intervention in terms of recovery capacity.
- H1A: There is a significant difference between repeated cold applications and the control intervention in terms of recovery capacity.

- H0A: There is no significant difference between immediate cold applications and delayed cold applications in terms of recovery.

H1A: There is a significant difference between immediate cold applications and delayed cold applications in terms of recovery.

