2.3 Investigation design

This study is a single-center, randomized, controlled trial with 3 arms. After the subjects have been admitted to the examination, they are divided into one of the 3 groups.

Group A: immediate cooling according to the muscle soreness protocol

Group B: delayed cooling according to the muscle soreness protocol (24 hours delayed)

Group C: Control group

This examination is a clinical trial of risk category A.

Group A: immediate cooling

In this group, cooling starts immediately after the muscle soreness protocol. Cooling is carried out 3 x /day both on the day of the muscle soreness protocol and for a period of 72 hours. Both thighs are cooled with the "Cold Hot Maxi Pack" from Axanova for a period of 20 minutes.

Cooling log: Day 1 (muscle soreness log, 3x/day), Day 2 (3x/day), Day 3 (3x/day), Day 4 (3x/day)

Group B: delayed cooling

In this group, cooling starts 24 hours after the sore muscle protocol. Cooling is also carried out 3 x /day for a period of 72 hours. Both thighs are cooled with the "Cold Hot Maxi Pack" from Axanova for a period of 20 minutes.

Cooling log: Day 1 (muscle soreness log, no cooling), Day 2 (3x/day), Day 3 (3x/day), Day 4 (3x/day).

Group C: Control group

This group receives according to the muscle soreness protocol and will not receive any cooling intervention, nor any other intervention, for the entire period thereafter.

Sore muscle protocol

To induce sore muscles, the test subjects perform one-sided, 6 times 12 – 15 knee extensors on an ergometer chair. They straighten and bend the knee as far as possible. They repeated the exercise 5 more times after a 2-minute break (a total of 6 rounds). The movement sequences are observed and corrected if necessary. A similar protocol has already been successfully used in the literature to induce muscle soreness (Ruas et al 2022, Comparison between eccentric-only and coupled concentric-eccentric contractions for neuromuscular fatigue and muscle damage). In order to increase the significance of the investigation, the subjects are asked not to carry out any additional interventions during the experimental phase.

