3.3 Investigation procedures

Investigation duration:

Subject to EC approval in 2024.

Recruitment period: January 2025

Conduct of the study: February - March 2025

Statistics and writing of the article: April – July 2025

Individual Investigation duration for each participant

Phase	Content	Time
Recruitment	Handing out patient information & consent, explanation of the experiment	30 min
Experiment Day 1	Anthropometry, baseline measurement, muscle soreness protocol (cooling: group A)	60 min
Experiment Day 2	Follow-up measurement 24 hours (Cooling: Group A and Group B)	30 min
Experiment Day 3	Follow-up measurement 48 hours (Cooling: Group A and Group B)	30 min
Experiment Day 4	Follow-up measurement 72 hours (Cooling: Group A and Group B)	30 min
Total time required per subject		180 min

Recruitment

As soon as the potential test subjects show interest in the study and arrive at the laboratory in Landquart, they are sent to the study director. If he is not present or available at that time, interested parties are asked to appear on another day.

The head of the study explains the procedure, the tests carried out, the risks and possible inconveniences. In addition, it is explained that participation is voluntary and that withdrawal is possible at any time, without giving reasons, without this having a negative impact on future care. The test subjects then receive the test subject information, which describes the examination in detail and in an understandable way. The document also contains a checklist that must be completed. The declaration of consent is also provided and must be signed and returned by the Director of Studies before the start of the programme. The doctor checks the completed checklist and confirms the consent.

Baseline measurements

The room temperature and relative humidity are determined at the beginning of each measurement day (Voltcraft MT52 digital multimeter, Hirschau, Germany). Baseline measurements include demographic data (age, gender, height). Anthropometric features at the beginning of the study included height (GPM Stadiometer, Zurich, Switzerland), body mass, and body fat percentage estimation. Body mass and lower body fat percentage were measured using

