4.2. Handling of missing data and drop-outs

Missing data, missed training sessions or abandonments are noted in the CRF. Data from patients who discontinue the examination is collected and stored. Drop-outs are not replaced by the recruitment of new participants. If consent is withdrawn, the data already collected will be included in the analysis for scientific and safety reasons. These are only anonymised after the analysis (Art. 32 ClinO-MD).

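### The sample size rests on t-tests of A-C and B-C, but the planned repeated-measures ANOVA names no deciding term or contrast, and the stated 80% power does not hold for A-C under the Bonferroni adjustment that the text claims

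*Combined protocol and SAP*

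**What the plan says.** The sample-size part of section 4.1 compares group A with control and group B with control. It assumes VAS means of 4.72 (control), 2.21 (A) and 1.87 (B), a common SD of 2.1, 13 per arm, and 15 per arm after 10% dropout. It attaches no time point to these means. The PASS table gives the Bonferroni setting as "none (divisor = 1" with alpha 0.05 on each row. The summary statement below it reads "The hypotheses are evaluated using two two-sided, two-sample methods. Bonferroni-adjusted t-tests with the same variance", with an overall type I error of 0.05 and at least 80% power for each comparison.

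The paragraph on the primary endpoints, later in section 4.1, describes a different analysis: "a repeated ANOVA analysis is carried out with a factor of 1: time (baseline, 24 hours, 48 hours, 72 hours", with intervention (A, B, C) as the second factor, at p < 0.05, for all recovery parameters. The synopsis agrees: "Repeated measure ANOVA, n=45 subjects".

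Section 2.1 poses two null hypotheses. One compares cooling with control, without saying whether A and B are pooled or tested separately. The other is "There is no significant difference between immediate cold applications and delayed cold applications in terms of recovery". On timing, section 2.3 says of group B "In this group, cooling starts 24 hours after the sore muscle protocol", and the schedule in section 3.3 lists "Follow-up measurement 24 hours (Cooling: Group A and Group B" without giving the order of that measurement and B's first session.

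**The concern.** The sample size answers two specific questions: does A differ from control, and does B differ from control? The planned ANOVA yields a group main effect, a time effect and a group-by-time interaction. None of these on its own says which arm differs. The plan does not say which term decides, so two analysts following section 4.1 could report different deciding tests on the same data. The trial is unblinded, so an open choice could be made after group results are visible.

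There is also an error in a stated figure. The summary promises at least 80% power with Bonferroni-adjusted tests at 13 per arm, but the PASS run that produced the 13 made no adjustment. Finally, A-B is a stated hypothesis with no named contrast and no power figure.

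**Working it through.** **Inputs, all from section 4.1:** SD 2.1; differences from control 2.51 (A) and 2.85 (B); n = 13 per arm; two-sided tests. The implied A-B difference is 2.21 − 1.87 = 0.34 cm.

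**1. The plan's own figure.** Power is that of a two-sample t-test (noncentral t, df = 2n − 2 = 24).
- Standard error: 2.1 × √(2/13) = 0.824.
- Noncentrality: 2.51/0.824 = 3.05 for A-C and 2.85/0.824 = 3.46 for B-C.
- At alpha 0.05 each, power is 0.83233 and 0.91287, which matches the PASS table. With n = 12, A-C falls to 0.799, so 13 is the minimum without adjustment.
- Dropout: 13/0.9 = 14.4, rounded up to 15 per arm. This also reproduces.

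**2. The error rate actually used.** With two tests at 0.05 that share a control arm, simulation under no effect gives a familywise error of about 9%, not the 5% overall that the summary states.

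**3. The error rate the summary claims.** Bonferroni means 0.05/2 = 0.025 per test.

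| Rule | Evaluable per arm | A-C power | B-C power |
|---|---|---|---|
| None, 0.05 each | 13 | 83.2% | 91.3% |
| Bonferroni, 0.025 each | 13 | 74.0% | 85.0% |
| Bonferroni, 0.025 each | 15 | 81.1% | 90.4% |
| Holm, 0.05 overall | 13 | about 81% | about 88% |

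The Holm row is from simulation with a shared control. Under Bonferroni, A-C needs 15 evaluable per arm, that is 15/0.9 = 16.7, or 17 per arm after 10% dropout.

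**4. A-B.** Noncentrality is 0.34/0.824 = 0.41, giving 6.8% power at alpha 0.05. The 95% CI half-width is t(0.975, 24) × 0.824 = 2.064 × 0.824 = 1.70 cm, five times the implied difference. About 600 per arm would be needed for 80% power.

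**5. What the ANOVA terms measure.** Randomisation makes the arms equal at baseline in expectation.
- If A's difference of 2.51 cm is present at all three follow-up visits, the main effect averages 0, 2.51, 2.51 and 2.51. That gives 3 × 2.51/4 = 1.88 cm, a dilution of one quarter.
- If the difference is present at one visit only, the main effect sees 2.51/4 = 0.63 cm.
- The interaction compares the time profiles and is not diluted by the baseline level. It is an omnibus test over three groups, so it does not identify the pair.

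The two terms can therefore disagree on one data set, and group B's start at 24 hours makes unequal time profiles likely by design.

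**The case against.** The best defence is that sizing a trial on a simpler test than the one used in the analysis is common and not in itself an error. The t-test sentence sits under the sample-size summary and may describe only the power model. The ANOVA is planned to examine differences between groups, so A-B is inside its omnibus test. This much stands: the ANOVA is valid, and what is missing is a named term and named contrasts. If instead the t-test sentence is meant as the analysis, section 4.1 holds two analyses that must be reconciled. The Bonferroni conflict remains on either reading.

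A reader might go further and infer that the ANOVA lacks power. The documents do not support that. They give no correlation between visits, so no power can be derived for it. As an illustration only, assume correlations of 0.3 to 0.7, equal SDs at all visits and the plan's VAS differences at all three follow-up visits. The interaction then has 83% power or more.

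A reader might also want fixed averaging windows, such as 24–72 h for A-C and 48–72 h for B-C, or a rule that VAS alone decides. Neither follows from the documents. The sizing names no visit, and an effect confined to one visit would shrink to a third in a three-visit average (2.51/3 = 0.84 cm). The Background stresses swelling and inflammation, so ranking the primary outcomes is the sponsor's decision and a separate matter. Sex restricts allocation but is not shown to be a needed model term. In section 4.2, "If consent is withdrawn, the data already collected will be included in the analysis for scientific and safety reasons" sits uneasily with an ANOVA that normally drops subjects with a missed visit. That is a tension, not a proven contradiction.

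**Conclusion.** The point holds and should be corrected before analysis. The tests that justify the sample size are not the tests planned for the primary endpoints, and the planned ANOVA leaves its deciding term, contrasts and visits open.

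One stated figure is wrong as written. Bonferroni-adjusted tests at 13 per arm give 74.0% power for A-C, not at least 80%; B-C, at 85.0%, meets the target. The 83.2% and 91.3% in the table hold only without adjustment, at a familywise error of about 9%. The A-B hypothesis is effectively untestable at the implied difference (about 7% power).

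These figures rest on the plan's own VAS means and SD, applied to a single mean with 13 evaluable per arm. They say nothing about power for the other primary outcomes, for which the plan gives no effect size or SD.

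**What to change.** 1. **One multiplicity rule for A-C and B-C.** Either use Holm at 0.05 overall (about 81% and 88% at n = 13 on the plan's VAS figures), or keep Bonferroni and restate A-C power as 74% at n = 13. Make the PASS table and the summary statement agree.
2. **Deciding contrasts.** Name A-C and B-C. Estimate them from a model of the 24, 48 and 72 h values, with that outcome's baseline as a covariate instead of a time level. Fix the deciding visit or visits in advance, allowing for B's start of cooling at 24 h and for the dilution that averaging brings if an effect is confined to one visit. Keep group by time as a supporting test and report every visit.
3. **A-B.** Report it as an estimate with a 95% CI and state that the trial is not sized to test it.
4. **The t-test sentence.** Label it as the power model.

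The cost is SAP wording, one model degree of freedom per outcome for the baseline, and possibly a less favourable stated power for A-C. No new subjects, visits or measurements are needed.
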